6.5 Drug Delivery System

6.5.1 Identity of Device

AeroFact™ is a drug /device combination product consisting of three basic components: (i) drug (SF-RI 1 bovine-origin surfactant); (ii) reusable device controller; and (iii) disposable single-patient, single-use drug delivery circuit and breath sensor. This is a stand-alone drug delivery system that integrates with a variety of nCPAP and nIMV devices and is not designed to be connected to the hospital network or the Internet. The AeroFact™ drug delivery system is designed to administer aerosolized surfactant to the lungs of spontaneously breathing premature infants receiving nCPAP or nIMV.

6.5.2 Aerosol Delivery System Components

The AeroFact drug delivery system (Figure 1) consists of reusable and single-patient elements:

6.5.2.1 Reusable Components

The controller is a multi-patient, reusable component with flat panel touch-screen display, electronics, and software. The controller has three core functions:

- To detect inspiration via a single-patient-use respiration sensor
- To advance suspension to the nebulizer via an integrated feed mechanism
- To generate aerosol during inspiration at the nCPAP interface

These functions occur in synchrony with the infant's inspiratory cycle. The flat panel touch-screen utilizes a graphical user interface (GUI) to allow the user to set and monitor delivery parameters, alarms, and system diagnostics. Visual and audible alarms are integrated into the controller. The

Pod communicates the signal from the disposable single patient use respiration sensor to the controller and breath synchronizes aerosol generation.

6.5.2.2 Single-patient disposable items:

Drug Reservoir (drug vial) is the reservoir, from which the drug product (lyophilized SF-RI 1) is reconstituted into a suspension and dispensed.

Drug delivery circuit is a disposable, single-patient circuit consisting of:

- Drug Feed Tubing which includes drug contacting components as follows: (i) luer connector (to VVAD) and (ii) tubing conveying drug suspension from the luer to the AF nebulizer.
- Vented Vial Access Device (VVAD) facilitates access to the drug reservoir and is provided to the user in an individual package.
- AF Nebulizer/nCPAP Interface uses a custom photo defined aperture plate (PDAP) vibrating mesh, which is unique in its ability to provide small droplet sizes and higher output rates. This is due to its innovative architecture, which provides up to 20-fold more apertures with smaller diameters than the conventional mesh. This meets the stringent requirements for efficient surfactant delivery to infants and represents enabling technology for the AeroFact platform. The AF nebulizer/nCPAP interface is designed to dispense aerosol proximal to the infant's airway and connect to conventional nCPAP systems.

Respiration Sensor is a separate sensor that is placed on the infant's abdomen which synchronizes drug delivery with the infant's breathing.

Ancillary non-investigational clinical supplies include the following:

- Nasal Prongs connect to the end of the drug delivery circuit and are provided in a variety of sizes to accommodate different size infants
- Knit cap/bonnet (F&PTM not shown) to secure the nasal prongs and nebulizer to the infant
- Cavilon™ no sting barrier film to protect the integrity of the skin prior to applying the breath sensor
- Kind™ Removal silicone tape to be placed over the breath sensor which secures it to the abdomen without comprising the integrity of the skin
- Study Medication Lock box
- Bedsheet clip

Refer to the AeroFact Drug Delivery System Directions for Use.

Figure1-AeroFact Drug Delivery System

6.5.3 Device Supply

Prior to AeroFact dosing, the drug delivery system will be brought to the bedside. The serial numbers for the controller/Pod and disposable drug delivery circuit will be recorded in the study records. A controller and Pod will be used by more than one patient and will be cleaned between each patient (see DFU). A new drug delivery circuit is required for each dose of AeroFact given and will never be re-used.

Used and unused disposable devices will be inventoried and returned to the Sponsor or Sponsor's designee. Drug Delivery Systems and their components will be returned to the Sponsor or Sponsor's designee at the conclusion of Part I.

6.5.4 Device Replacement

One device (controller, drug delivery circuit and associated components) is expected to perform throughout the duration of dose. If the controller or the drug delivery circuit are not functioning optimally for any reason, instructions for trouble-shooting provided in the device instruction manual should be followed by the trained unblinded staff. If one or more devices need to be

replaced, the reason should be documented in the patient's medical record and appropriate study records. Additional devices are provided for this purpose. The unique serial numbers of the new controller and drug delivery circuit will be recorded in the patient's medical record and study records.

Controllers and drug delivery circuits should be replaced at any time if there is a confirmed or suspected malfunction.

- Device substitution, whether controller or circuit, should be recorded on the appropriate page of the study records.
- Notation must be made if the investigator suspects the device is not performing optimally for any reason.

If the Device fails, there is no way to restart a partial dose.

- For any partial dose delivered, note the amount of dose remaining on the controller drug delivery screen (if available) and record on Unblinded dosing record. Otherwise estimate the amount delivered and record on Unblinded dosing record. This will count as one of the 4 delivered doses. Patient will be eligible for repeat dosing 2 hours after the start of the previous dose.
- Only a maximum of four doses of AeroFact will be delivered.

For device performance problems or complaints, the Sponsor or the Sponsor's designee should be contacted within 48 hours. Complaints should be submitted to: [contact]. Failed devices and drug delivery circuits will be inventoried and returned to the Sponsor or the Sponsor's designee.

6.6 Blinding

Clinical and research staff will remain blinded to dose level being administered with the exception of pharmacy staff or designee and respiratory therapy staff or designee. AeroFact drug delivery circuit will remain in line for the duration of dosing or a minimum of 2 hours, regardless of dose volume being administered.

6.7 Concomitant Medication/Therapies of Interest

Concomitant medications of interest will be collected for all enrolled infants. Concomitant medications of interest include: corticosteroids, methylxanthines, continuous infusion vasopressors, vitamin A, bolus surfactant and medications for the prophylaxis or treatment of PDA administered to the patient during the course of the study (starting on Day 1) will be recorded on the Concomitant Medications CRF. Blood products and surgeries will also be recorded. The Investigator will record any AE on the AE CRF for which a concomitant medication/therapy was administered during Part I only.

6.7.1 Discouraged Concomitant Therapy

The use of Vitamin A or corticosteroids for BPD prophylaxis must be consistent, and appropriate for age, for all enrolled infants within each study site.

The routine use of hydrocortisone as first-line therapy for BP/adrenal support should be avoided during the first 96 hours of life. Clinical guidelines for use of glucocorticoids can be found in the Manual of Procedures (MOP).

Potential candidates for initiation of glucocorticoids for hypotension will include inadequate response to vasopressor therapy (dopamine \geq 20 mcg/kg/min \pm dobutamine or epinephrine) with either:

- Persistent hypotension despite fluid resuscitation, or
- Inability to wean medications for > 48 h
and
- No contraindications to glucocorticoid therapy

6.8 Investigational Product (IP) Supplies and Accountability

Investigational Product (IP) supplies will not be sent to the Investigator(s) until the following documentation has been received by the Sponsor:

- Written proof of approval of the protocol and its informed consent forms (ICFs) by the Independent Review Board (IRB) for the institution where the study is to be conducted.
- An Investigator-signed and dated FDA Form 1572.
- A signed and dated curriculum vitae (CV) of the Principal Investigator including a copy of the Principal Investigator's current medical license (required in the US).

The Sponsor may send components of the IP in advance of the completion of the regulatory documents if those components are for training purposes only. In these cases, the Sponsor should send documentation to the site instructing them that the IP components are for training purposes only and screening and enrolment may not begin until an SIV is completed and a favourable IRB approval has been granted. The Investigator and study staff will be responsible for the accountability of all investigational product study supplies (dispensing, inventory, and record keeping) following Aerogen Pharma instructions, adhering to Good Clinical Practice (GCP) guidelines and local and/or regional requirements.

Under no circumstances will the Investigator allow the study investigational products or ancillary components to be used other than as directed by this protocol. Study investigational product will not be administered to any individual who is not enrolled into the study.

An accurate and timely record of the receipt of all study investigational product; dispensing of study investigational product to the patient; collection of unused study investigational product; and subsequent return of unused study investigational product to Aerogen Pharma (or designee) must be maintained. This includes but may not be limited to: (a) documentation of receipt of study investigational product, (b) study investigational product dispensing/return reconciliation log, (c) study investigational product accountability log, (d) all shipping service receipts, and (e) documentation of returned study investigational product to the Sponsor. All forms will be provided by Aerogen Pharma. Any comparable forms that the investigational site wishes to use must be approved by Aerogen Pharma.

The supplies and inventory records must be made available, upon request, for inspection by the designated representative of Aerogen Pharma, a representative of the FDA, or a representative of a non-US health authority. All unused study investigational product, including empty containers are to be returned to Aerogen Pharma at the conclusion of the study, unless provision is made by Aerogen Pharma for destruction of supplies and containers at the investigational site. Upon completion of study investigational product accountability and reconciliation procedures by investigational site personnel and documentation procedures by Aerogen Pharma personnel, study investigational product that is to be returned to Aerogen Pharma, if necessary, must be boxed and sealed and shipped back to Aerogen Pharma following all local regulatory requirements.

7 EFFICACY ENDPOINTS

7.1 Primary Efficacy Endpoint – Part I

- Proportion of infants requiring intubation/cannulation and bolus surfactant instillation in the first 7 days after birth

7.2 Secondary Efficacy Endpoints – Part I

- Time to first intubation/cannulation and bolus surfactant instillation between study treatments for first 7 days of life
- Compare the proportion of infants across groups receiving multiple doses of surfactant.
- Number of days on mechanical ventilation from the day of birth to 40 weeks PMA or discharge.
- Number of days on supplemental oxygen administration from the day of birth to 40 weeks PMA or discharge
- Survival without bronchopulmonary dysplasia (BPD) at 36 and 40 weeks PMA

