2.2.3 Summary of Clinical Results

2.2.3.1 APC-AF-CLN-001-Safety Analysis Conclusions:

- The overall incidence of TEAEs was low among AeroFact patients; 3 patients (30%) had 1 or more TEAE(s) in Part I, and 5 patients (23.8%) had 1 or more TEAE(s) in Part II.
- There were no TEAEs which were assessed by the Investigator as related to the study drug, device, or procedure, and none led to premature discontinuation from the study drug or premature discontinuation from the study.
- The most common TEAEs reported were patent ductus arteriosus occurring for 1 patient (10%) in Part 1 and for 3 patients (9.5%) in Part II, and pneumothorax occurring for 1 patient (10%) in Part 1 and 1 patient (4.8%) in Part II.
- All TEAEs in Part I were mild and the majority of TEAEs in Part II were mild with a severe TEAE occurring in 1 patient (4.8%) (pulmonary hemorrhage identified after intubation).
- During Day 1 to study Day 4, following AeroFact dosing, there was 1 occurrence (10%) of moderate nasal congestion in Part I, and 5 occurrences (23.8%) of moderate nasal congestion and 1 occurrence (4.8%) of severe nasal congestion in Part II of the study. Nasal aspiration occurred in 2 patients (9.5%) in Part II on Day 1 in the study. Neither nasal congestion or nasal aspiration data were available from the historical control patients for comparison.
- One patient in Part I and 1 patient in Part II of the study had an SAE. Both patients had the SAE of culture-proven sepsis, which was not related to the study drug, the device, or the procedure, did not emerge during the treatment period, and resulted in death.
- Generally, the incidence of AEs associated with dosing tolerance in the first 24 hours was low; the incidence of AEs for AeroFact only vs. AeroFact plus bolus surfactant demonstrated comparability.
- The incidence of post-dose comorbidities of prematurity and AEs was low and consistent between the patients treated with AeroFact vs. historical controls.

2.2.3.2 APC-AF-CLN-001-Efficacy Analysis Conclusions:

- At 36 Weeks PMA, a larger proportion of patients receiving AeroFact in Part I and Part II of the study survived without BPD (88.9% and 78.9%, respectively) compared with Part I and Part II historical control patients (73.3% and 66.7%, respectively).
- The median (range) length of stay in the NICU for AeroFact patients in Part I and Part II was comparable to historical control patients.

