7.3 Additional Efficacy Endpoints – Part II

- Assessment of pulmonary outcomes at 3, 6, 9 and 12 months corrected age
- Length of NICU Stay (LOS)
- Proportion of subjects with any respiratory resource utilization at 3, 6, 9 and 12 months corrected age
- Respiratory morbidity per quarter till 12 months corrected age
- Assessment of modified GMFS at 12 months corrected age

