12.9.1 Intent-to-Treat (ITT) population

The Intent-to-Treat (ITT) population is defined as all randomized subjects. The ITT population will be the primary population for the primary, secondary and additional efficacy analysis.

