12.12 Statistical Methods

A Statistical Analysis Plan (SAP) will be developed and approved before the database is locked. The SAP will present the detailed statistical methodology to be used in analyzing the efficacy and safety data from this trial. All inferential statistical analysis will be based on a two-sided test with a Type I error rate of 0.05.

All the efficacy analyses presented here will be conducted using both ITT and PP populations. All safety analyses will be conducted using the Safety population. All data collected will be summarized according to the variable type.

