12.13 Efficacy Analyses

The primary analyses of the primary and secondary efficacy endpoints will be conducted on the ITT population. The PP population analyses of primary and secondary endpoints will be considered supportive.

For the efficacy endpoints the data will be summarized and compared according to the variable type:

- Continuous data summaries will include:
 - Descriptive summary of number of observations, mean, standard deviation, median, and minimum and maximum values.
 - Analysis of Covariance (ANCOVA) or Mixed Model Repeated Measures (MMRM) adjusted for stratification factors for inferential statistics.
- Categorical data summaries will include:
 - Frequency counts and percentages
 - Logit model or Generalized Estimating Equation (GEE) method adjusted for stratification factors and clustering of multiple births within a mother for inferential statistics
- Time-dependent data: Cox proportional hazards model will be used to analyze time dependent data and to depict the time to event data.

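### Ventilation days, oxygen days and length of stay have no rule for infants who die, and the default comparison of raw day totals can favour the arm with more deaths on two of the three and loses power on the other

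*Combined protocol and SAP*

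**What the plan says.** Section 7.2 (repeated in the Synopsis and 12.2.2) lists two day totals among the Part I secondary endpoints: "Number of days on mechanical ventilation from the day of birth to 40 weeks PMA or discharge" and "Number of days on supplemental oxygen administration from the day of birth to 40 weeks PMA or discharge". LOS in the NICU appears in 7.3 and 12.2.3 among the additional endpoints. None of these sections says what value an infant who dies receives. The same secondary list includes "Survival without bronchopulmonary dysplasia (BPD) at 36 and 40 weeks PMA", which does count death as failure.

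Section 12.9.1 keeps every infant in the analysis: "The Intent-to-Treat (ITT) population is defined as all randomized subjects". Section 12.13 assigns methods by type of variable. For continuous data it names "Analysis of Covariance (ANCOVA) or Mixed Model Repeated Measures (MMRM) adjusted for stratification factors for inferential statistics"; categorical data get a logit or GEE model and time-to-event data a Cox model. Clustering within a mother is mentioned only for categorical data. Section 12.11 puts the secondary endpoints under a closed test procedure, with the order left to the SAP. Section 12.12 defers the detail: "The SAP will present the detailed statistical methodology to be used in analyzing the efficacy and safety data from this trial".

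**The concern.** On all three measures fewer days reads as better. An infant cannot accrue days after death, so unless a rule says otherwise an infant who dies on day 10 contributes at most 10 oxygen days and a 10-day stay. In this population survivors may have several weeks of each, so a death pulls the arm mean in the favourable direction. Oxygen days sit in the Type I-controlled secondary family, so a mortality imbalance could feed a formal claim.

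Ventilation days raise a different issue. Most infants may have zero days and the rest a long right tail. A comparison of means is then driven by a few long stays on the ventilator and is insensitive to a change in how many infants are ventilated at all, which is the effect the trial is designed around.

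Deaths are plausible. Section 2.2.3 reports one serious adverse event in each part of the Phase 2a study, both sepsis, which "did not emerge during the treatment period, and resulted in death".

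**Working it through.** **The plan's own figure.** The only sample-size figure is for the primary endpoint. With 40% versus 20%, two-sided 0.05 and 80% power:

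n = [1.960 × √(2 × 0.30 × 0.70) + 0.842 × √(0.40 × 0.60 + 0.20 × 0.80)]² / 0.20² = (1.270 + 0.532)² / 0.04 ≈ 81.2, so 82 per arm; 82 / 0.95 = 86.3, so 87 randomized.

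This matches 12.3. No figure is given for the day counts, so what follows rests on stated assumptions. The simulations use 87 per arm, 3,000 or 4,000 runs per setting, and treat infants as independent.

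**Which method applies.** Each infant has one day total. It is neither categorical nor a time to event, and MMRM needs repeated values. ANCOVA is what remains of 12.13.

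**Mortality.** Phase 2a: 2 / (10 + 21) = 6.5%, exact 95% CI 0.8% to 21.4%. The illustration uses 3% versus 10%, about 2.6 and 8.7 deaths among 87.

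**LOS.** If survivors average L days and a fraction d die on day t, the arm mean shifts by −d × (L − t). With t = 5 and L from 40 to 70:
- d = 3%: 0.03 × 35 = 1.1 to 0.03 × 65 = 2.0 days lower
- d = 6.5%: 0.065 × 35 = 2.3 to 0.065 × 65 = 4.2 days lower

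Simulation with survivor mean 55, SD 20, deaths on days 2–10 and no effect in survivors gives this chance of a significant result favouring the higher-mortality arm (nominal 2.5%):

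| Deaths | As counted | Death ranked worst |
|---|---|---|
| 3% vs 3% | 2.2% | 2.6% |
| 3% vs 6% | 6.1% | 0.8% |
| 3% vs 10% | 17% | 0.2% |
| 2% vs 12% | 28% | 0.0% |

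With deaths spread over days 3–25, the 3% versus 10% figure is about 14%.

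**Oxygen days.** Assume a gamma distribution (mean 30, SD 22, capped at 75), deaths on days 3–25 and no effect in survivors. The mean is 29.2 with no deaths and 28.2 with 6.5% deaths as counted. Giving each death the full 75 days adds 0.065 × (75 − 29.2) = 3.0, so 32.2. At 3% versus 10% deaths, a significant result favouring the higher-mortality arm occurs in about 6% of trials as counted and 0.2–0.3% with death ranked worst.

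**Ventilation days, direction.** Assume 30% ever ventilated (log-normal, median 4 days, log-SD 1.2) and deaths ventilated until days 2–10. At 3% versus 10% deaths the observed mean difference is +0.27 days against the higher-mortality arm. Had those infants lived and been ventilated for 30 days it would be +1.92. The harm is understated but not reversed.

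**Ventilation days, power.** The escalation rates in 12.3 (40% versus 20%) stand in for the share ever ventilated.
- No deaths, median 3 or 6 days, log-SD 0.8 to 1.6: ANCOVA on raw days 30–56%, on ranks 84–85%. Type I error of raw ANCOVA is 3.6–4.8%.
- 3% deaths, median 4 days, log-SD 1.0 to 1.5: mean-based test about 31–45%, stratified rank test with death worst 73–75%.

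**Support-free days to 40 weeks PMA, as an alternative.** The window is 14 weeks = 98 days for an infant born at 26 0/7 and 57 days at 31 6/7. Within each stratum it still varies by 20 days (98 to 78, and 77 to 57). A never-ventilated infant scores the full window, so the ranks mostly sort infants by gestational age. In the same 3%-death setting, with gestational age uniform over 26–32 weeks and death scored 0, power is about 15–17%.

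**The case against.** The strongest reply is that 12.13 never assigns ANCOVA to these endpoints by name, and that 12.12 leaves methods and conventions to an SAP whose text was not available here. That stands as a limit: the SAP may already hold a death rule. It does not remove the point, because the protocol's own wording leads to ANCOVA on raw totals and 7.2 defines the counts without a rule.

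Several stronger readings are tempting and the documents do not support them:
- *That the protocol stops the count at death.* It names only 40 weeks PMA or discharge. Stopping at death is the default that follows from silence.
- *That an early death is a good result on ventilation days.* An infant ventilated until an early death scores above the many zeros. Only oxygen days and LOS reward the death.
- *That ANCOVA produces false positives here.* At equal mortality it does not. The loss is in power and interpretability.
- *That LOS shares all these problems.* It is an additional endpoint, outside the controlled secondary family, and not zero-heavy.
- *That the planned calls already supply oxygen days after discharge.* Sections 10.1.5.2 and 10.1.5.3 have them verify support status; the last day on oxygen is a discharge item in 10.1.5.4.

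It is also fair that the oxygen bias is modest: a 1.0-day shift against a standard error of about 2.9 days. The Phase 2a mortality comes from 31 infants with gestational age capped at 30 6/7 weeks. The 40% and 20% are not ventilation rates, since the primary endpoint includes cannulation. Finally, survival without BPD already counts death.

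**Conclusion.** The concern holds as a cheap improvement, not as a flaw in the trial's main result. Three duration endpoints lack a death rule while ITT keeps deaths in. Under an assumed imbalance of 3% versus 10%, the higher-mortality arm is wrongly favoured in about 6% of trials on oxygen days and 14–17% on LOS, where 2.5% is nominal. With equal mortality there is no such bias. On ventilation days death is under-penalised, and the raw-mean comparison has roughly half the power of a rank test, or less in the more skewed settings.

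The power gap depends on treatment changing whether infants are ventilated. An effect only on duration among the ventilated was not examined and would favour ranks less. All durations, and the death rates in the illustration, are assumptions. The primary endpoint and the 261-infant sample size are unaffected.

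**What to change.** In 7.2, 7.3 and 12.13 (and the matching Synopsis and 12.2 text), before unblinding:

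1. Keep the day counts. Rank death before 40 weeks PMA or discharge as the worst outcome on all three.
2. Test with a gestational-age-stratified rank test, or a proportional-odds model that allows for clustering by mother. Siblings share an assignment (12.4), yet 12.13 provides for clustering only in categorical data. Keep means as description.
3. For infants discharged on oxygen, either state that the endpoint covers in-hospital days only, or add a stop-date question to the 36- and 40-week calls.
4. Do not replace the counts with support-free days to 40 weeks PMA. If a support-free endpoint is wanted, use a fixed-length window from birth, such as 28 days, so that every never-supported survivor has the same score.

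The cost is endpoint and SAP wording, plus possibly one call question. The price in interpretation is that the effect becomes a rank or odds measure rather than a difference in mean days.
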